#### **4.2.14 Previous vs. concomitant medication**

Previous medications are those medications taken at least once before the first treatment of the patient. Concomitant medications are those medications taken at least once at/after the first treatment of the patient.

#### **4.2.15 Adverse events**

AEs with onset during or after administration of first study medication (study day 1) are defined as treatment emergent.

### **5 Blind Data Review Meeting**

A BDRM will be held prior to database hard lock/unblinding where **AMS** and Sponsor representatives will assess protocol deviations as major or minor with regard to their influence on any of the analysis variables and to determine patient inclusion in the analysis sets.

The **AMS** biostatistician will prepare blinded review listings. Deviations not apparent in the clinical database (e.g. findings during monitoring of the investigational site) will be contributed by the sponsor's clinical project leader.

The decisions of the BDRM will be documented in writing and will be approved by signature of the attendees and may potentially amend methodology/analysis set definitions planned in this SAP.

The discussion in the review meeting will include but may not be restricted to the following topics:

- Violations of the study protocol including violations of inclusion/exclusion criteria
- Identification of patients randomised but not treated
- Impact assessment of prohibited medications
- Patients without efficacy data
- Patients where blind was broken prior to formal unblinding of the study
- Procedural deviations at the trial sites which are not reflected in the clinical database
- Premature patient discontinuations (reason and timing).
- Patients with COVID-19
- Patients with Week 16 visit window violations
- Assessment of impact of the COVID19 pandemic on visits occurring during COVID19 pandemic vs. other visits

Full details on the reviews performed and the decisions made in the BDRM will be given in the BDRM protocol.

## 6 General Methodology

All analyses will be performed using SAS Version 9.4 or higher.

If not mentioned otherwise analyses will be stratified by treatment group displaying the following treatment groups (in this ordering): DS107, Placebo, Total. Therefore treatment will not be mentioned explicitly as stratification variable usually.

All eCRF data will be listed, therefore listings may not be mentioned explicitly.

In listings the patient's screening number will be used as the main patient identifier. Usually listings will be sorted by treatment, patient's screening number and (if applicable) visit/point in time.

### 6.1 Primary Endpoint Evaluation

The primary endpoint variables will be:

- the proportion of patients achieving an vIGA-ADTM score of 0 (clear) or 1 (almost clear) and a decrease of at least 2 points in vIGA-ADTM from baseline to Week 16.
- the proportion of patients achieving EASI-75 ( $\geq 75\%$  improvement from baseline) at Week 16.

Both primary endpoints will be analysed using a Generalised Linear Mixed Model (GLMM) with treatment arm, visit, their interaction treatment-by-visit, and baseline vIGA-ADTM value as factors, and with patient as random effect; this model will especially be used to estimate missing data and the treatment effects at Week 16 taking missing data into account. The primary analysis will be based on the FAS, and repeated for the PPS as a supportive sensitivity analysis. Success in either of the primary endpoints denotes successful proof of efficacy.

If rescue medication is used, the patient will be specified as a non-responder from the time the rescue is used.

The handling of missing data in regards with primary statistical analysis and further sensitivity analysis using the jump to reference method to estimate the de facto estimand and analysing patients who received rescue medication as treatment failures are described in section 4.1.5.

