### 8.3.1 Baseline (Visit 2)

**Note: it must be ensured that inclusion criteria regarding the severity of the disease remain relatively unchanged since screening in order to exclude patients responding to the emollient use since screening visit i.e. IGA score must be unchanged and EASI score should not change by more than 10%.** Patients will attend the investigational site at Visit 2 when the following procedures/assessments will occur.

- Verification of inclusion/exclusion criteria (Sections 7.2 & 7.3)
- Patient Randomisation (as detailed in Section 10.5)
- Samples for clinical laboratory safety tests (haematology and serum biochemistry as detailed in Section 9.2.4)
- Pharmacokinetic Sampling (as detailed in Section 9.2.9)
- Biomarker Sampling (as detailed in Section 9.2.10)
- Vital signs (blood pressures, heart rate and body temperature), as detailed in Section 9.2.3);
- Physical examination (as detailed in Section 9.2.2)
- Electrocardiogram (ECG) (as detailed in Section 9.2.7)
- Dispense Study Drug
- Dispense Patient Compliance Log
- Body Surface Area (as detailed in Section 9.1.4)
- Validated Investigator's Global Assessment (as detailed in Section 9.1.1)
- Eczema Area and Severity Index (EASI) (as detailed in Section 9.1.2)
- NRS Pruritus assessment (as detailed in Section 9.1.3)
- Dermatology Life Quality Index (DLQI) Questionnaire (as detailed in Section 9.1.5)

- Patient Orientated Eczema Measure (POEM) questionnaire (as detailed in Section 9.1.6)
- SCORing AD (SCORAD) questionnaire (as detailed in Section 9.1.7)
- Athens Insomnia Scale (AIS) (as detailed in Section 9.1.8)
- Patient- Orientated SCORAD questionnaire (as detailed in Section 9.1.9)
- Concomitant medication assessment (as detailed in Section 9.2.13)
- Review emollient usage and capture
- AE assessment (as detailed in Section 11)

If all study entry criteria are satisfied the Investigator will randomize the patient and provide the patient with the DS107 capsules or placebo capsules from one of the patient treatment packs available at the site (allocated via the central randomization).

The first administration of DS107 or placebo will be carried out after the Baseline visit. Following this DS107 capsules or placebo medication will be administered once daily. IMP will be administered approximately 2 hours after food consumption at the same time each day. Patients will be instructed to not consume food for approximately 1 hour after IMP administration.

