### 12.2 Randomisation

Approximately 220 patients will be randomized into double-blind treatment groups in a 1:1 ratio by an IWRS.

- 2g DS107 (4 DS107 capsules) administered once-daily for 16 weeks
- Placebo (4 placebo capsules) orally administered once-daily for 16 weeks

A randomization list permuted by blocks and stratified by site will be generated by the Sponsor or its designee. The randomization schedule with study drug assignments will be generated prior to the start of the study and will be known only to the individuals responsible for labelling the study drug, the statisticians generating the schedule and the IWRS team responsible for implementing the schedule. The IWRS will assign a medication kit number to each patient and the contents will be based on the randomization code.

At the investigational site, each patient will be assigned a patient identifier number during screening that will be used on all patient documentation. The patient identifier number will contain the site number and the patient number assigned in numerical order at the Screening Visit (e.g.: 102-10 for the tenth patient screened at the site number 02). Patient numbers will be assigned in ascending order starting with 01.

The treatment assignment procedure will use blocks of sufficient size to maintain a blind and balance across treatment arms. Following successful completion of the screening/baseline evaluations and confirmation that the patient is eligible for participation, the patient will be randomised to treatment. This will be performed by the Investigator using the IWRS which will assign a medication number to the patient.

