### 12.8.2 Primary variables

The primary variables will be:

- the proportion of patients achieving a vIGA-AD™ score of 0 (clear) or 1 (almost clear) and a decrease of at least 2 points in vIGA-AD™ from baseline to Week 16.
- the proportion of patients achieving EASI-75 ( $\geq 75\%$  improvement from baseline) at Week 16.

Both primary endpoints will be analysed using a Generalised Linear Mixed Model (GLMM) with treatment arm, visit, their interaction treatment-by-visit, and baseline vIGA-AD™ value as factors, and with patient as random effect; this model will especially be used to estimate missing data and the treatment effects at Week 16 taking missing data into account. The primary analysis will be based on the FAS, and repeated for the PPS as a supportive sensitivity analysis. Success in either of the primary endpoints denotes successful proof of efficacy.

If rescue medication is used, the patient will be specified as a non-responder from the time the rescue is used.

The primary statistical analysis assumes “Missing At Random (MAR)” when handling missing data. The treatment effect obtained under the MAR assumption is essentially that which could have been reached if all patients had fully adhered to treatment or, in other words, the effect a patient may expect if they take the medication as directed. This is sometimes known as the ‘de jure’ or ‘efficacy’ estimand. Due to the lack of perfect adherence in practice, the ‘de facto’ or effectiveness treatment effect will also be estimated. This estimand includes assumptions regarding the treatment effects that could be expected to occur when patients discontinue treatment. The *jump to reference* method described by Carpenter *et al.* (2013) will be used to estimate the de facto estimand, using the placebo arm as the reference. This is based on the assumption that patients who discontinue from study drug have no alternative oral treatment option suitable for longer-term use and so their responses are likely to revert to those of the placebo group. An additional sensitivity analysis will evaluate patients who received rescue medication as treatment failures from the visit onwards where rescue treatment started. The sensitivity analyses for missing data will be performed on the FAS only.

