### 12.8.3 Secondary variables

IGA and EASI-75 responders at other time points will also be analysed using a GLMM model similar to that described in Section 12.8.2.

The efficacy variables and their changes from baseline will be summarized with descriptive statistics per treatment group and visit. This applies to the vIGA-AD™, EASI, NRS scores for pruritus, DLQI, POEM, SCORAD, AIS and PO-SCORAD. Change from baseline endpoints will be analysed using Mixed Model with Repeated Measures (MMRM) with Treatment Arm, Visit and Treatment x Visit Interaction as a factors and baseline value as a covariate, to account for missing data. The secondary efficacy analyses will be based on the FAS only. For vIGA-AD™ as a 5-level ordinal variable, mixed ordinal logistic regression will be used with factors defined as above and IGA at baseline as a factor too.

If rescue medication is used, the patient will be specified as a non-responder from the time the rescue is used

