## 2 Sample Size

In the Phase 2a trial, IGA response rates of 21.6% and 11.8% were observed for DS107 and placebo respectively resulting in a difference in response rates of 9.8%. Due to the prolonged treatment period of 16 weeks, a clinically relevant difference in IGA response rates of 15% was expected for the current study.

Assuming a placebo response rate of 12% and a true response rate difference of 15% at Week 16 and using a two-sided Chi-Square test on a significance of 5%, then 220 evaluable patients (110 patients per treatment arm) will be needed for 80% power to detect this difference as statistically significant. As the following table shows, the number of patients needed for the discovery of a 15% response rate difference depends also on the placebo response rate shown in the left column of the table as decimal numbers:

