### 7.3 Efficacy - Secondary Endpoints Evaluation

All secondary efficacy analyses will be performed as described in chapter 6.2 with the FAS only.

IGA and EASI-75 responders at other time points will also be analysed using a GLMM model similar to that described in Section 6.1.

The efficacy variables and their changes from baseline will be summarized with descriptive statistics per treatment group and visit. This applies to the vIGA-ADTM, EASI, NRS scores for

pruritus, DLQI, POEM, SCORAD, AIS and PO-SCORAD. Change from baseline endpoints will be analysed using Mixed Model with Repeated Measures (MMRM) with Treatment Arm, Visit and Treatment x Visit Interaction as a factors and baseline value as a covariate, to account for missing data. For vIGA-ADTM as a 5-level ordinal variable, mixed ordinal logistic regression will be used with factors defined as above and IGA at baseline as a factor too.

If rescue medication is used, the patient will be specified as a non-responder from the time the rescue is used.

The following parameters will be analysed as described above:

- Proportion of patients achieving a vIGA-ADTM score of 0 (clear) or 1 (almost clear) and a decrease of at least 2 points in vIGA-ADTM in treated population compared to placebo population from baseline to Week 4, 8, 12, 18 and 20
- Change in proportion of patients achieving a vIGA-ADTM score of 0 (clear) or 1 (almost clear) and a decrease of at least 2 points in vIGA-ADTM in treated population compared to placebo population from Week 16 to Week 18 and 20.
- Absolute proportion of patients achieving EASI-75 ( $\geq 75\%$  improvement from baseline) in treated population compared to placebo population at Week 4, 8, 12, 18 and 20
- Change from baseline in vIGA-ADTM score in treated population compared to placebo population to Week 4, 8, 12, 16, 18 and 20
- Change from Week 16 in vIGA-ADTM score in treated population compared to placebo population to Week 18 and 20.
- Change from baseline in EASI in treated population compared to placebo population to Week 4, 8, 12, 16, 18 and 20
- Change from Week 16 in EASI in treated population compared to placebo population to Week 18 and 20.

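### The primary GLMM leaves out site, the only stratification factor, and adjusts EASI-75 for baseline vIGA-AD but not baseline EASI; adding both costs no data and gains a little power

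*SAP*

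**What the plan says.** **Randomisation.** Protocol 12.2 states: "A randomization list permuted by blocks and stratified by site will be generated by the Sponsor or its designee". Protocol 10.5 and SAP 1.5 agree. No other stratification factor is named.

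**Primary model.** SAP 6.1 states: "Both primary endpoints will be analysed using a Generalised Linear Mixed Model (GLMM) with treatment arm, visit, their interaction treatment-by-visit, and baseline" vIGA-AD. Protocol 12.8.2 ends the same sentence with "baseline vIGA-AD™ value as factors, and with patient as random effect". One model serves both primary endpoints.

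**Secondary models.** SAP 7.3 carries the model to the other visits: "IGA and EASI-75 responders at other time points will also be analysed using a GLMM model similar to that described in Section 6.1". For the change-from-baseline endpoints, Protocol 12.8.3 lists treatment, visit and their interaction "as a factors and baseline value as a covariate, to account for missing data". Change in EASI is therefore adjusted for baseline EASI. Site is not in these models either. The SAP's analyses use centre only to count patients per analysis set (SAP 7.6).

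**Available data.** The Visit 2 list in Protocol 8.3.1 includes "Eczema Area and Severity Index (EASI) (as detailed in Section 9.1.2"). The patient identifier contains the site number (Protocol 10.5). Inclusion criteria 2 and 3 require a baseline vIGA-AD of 3 or 4 and an EASI of at least 16; the EASI scale runs to 72.

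**Power.** SAP 2 sizes the trial "using a two-sided Chi-Square test on a significance of 5%, then 220 evaluable patients", with 110 per arm and 80% power at 12% versus 27%.

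**The concern.** Blocking within site balances the arms inside each site. If sites differ in response rate, that balance makes the estimated treatment effect more precise than a model without site recognises. The standard error is then too large, the test rejects slightly less often than 5% under the null, and power is lost. If sites differ little, nothing is lost.

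The EASI-75 model has a similar gap. Its only severity covariate has two levels, while the continuous score from which the endpoint is calculated is not used. Leaving it out does not disturb type I error, but may cost some power if baseline EASI predicts response.

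The plan is also inconsistent with its own practice. It adjusts change in EASI for baseline EASI but not EASI-75, which is a primary endpoint. The sponsor's Phase 2a responder analysis by severity group was stratified for site (Protocol 1.6), whereas this trial randomises by site and then drops it.

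**Working it through.** **1. The plan's own figure.** Inputs from SAP 2: p1 = 0.12, p2 = 0.27, two-sided alpha 0.05, 80% power. The pooled-variance chi-square formula, with p̄ = 0.195, is

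n per arm = [1.960·√(2·0.195·0.805) + 0.842·√(0.12·0.88 + 0.27·0.73)]² / 0.15² = [1.960·0.5603 + 0.842·0.5502]² / 0.0225 = 108.3.

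The table gives 108.4. Both round up to 109, and the plan uses 110. Power at 110 per arm is Φ[(√(110·0.0225) − 1.960·0.5603)/0.5502] = Φ(0.863) = 80.6%. The figure reproduces, and it contains no covariate adjustment.

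**2. Rough size of the gain.** If the added terms explain a share R² of the outcome variance, 110 patients act like 110/(1 − R²):

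| R² | Effective n per arm | Power |
|---|---|---|
| 0 | 110.0 | 80.6% |
| 2% | 112.2 | 81.4% |
| 5% | 115.8 | 82.6% |
| 10% | 122.2 | 84.6% |

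**3. Simulation of the planned type of model.** 220 patients; Weeks 4, 8, 12 and 16; random patient intercept; baseline vIGA-AD; 12% versus 27% at Week 16; maximum-likelihood fit; Wald test of the Week 16 treatment effect. Both models were fitted to the same data sets. The documents do not give the remaining inputs, so these are assumptions: patient SD 2.0 on the logit scale, 35% with baseline vIGA-AD 4, blocks of 4, unequal site sizes, 3% dropout per visit, and 19.5% response in both arms under the null.

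*Site random intercept added, 20 sites, 3,000 trials per row:*

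| Site ICC | Power without / with | Gain (points) | Type I error without / with |
|---|---|---|---|
| 0.05 | 77.6% / 78.2% | 0.7 | 5.1% / 5.3% |
| 0.10 | 76.6% / 77.8% | 1.3 | 4.1% / 4.6% |
| 0.20 | 76.2% / 79.1% | 2.9 | 4.1% / 5.0% |

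Gains come from unrounded powers. Simulation error is √(0.05·0.95/3000) = 0.4 points for type I error and 0.2 to 0.4 points for the paired gains. At ICC 0.20 with 1,500 trials, 10 sites gain 3.3 points (type I error 4.3% / 5.0%) and 40 sites gain 2.7 points (3.2% / 3.9%).

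*Baseline EASI added next to baseline vIGA-AD, assumed correlation 0.5, no site effect, 3,000 trials each:*

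| Log-odds ratio per SD | Gain at 12% vs 27% | Gain at 30% vs 45% (assumed rates) |
|---|---|---|
| 0.3 | 0.4 | 0.7 |
| 0.5 | 1.2 | 1.0 |
| 0.8 | 2.6 | 4.3 |

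Type I error without / with EASI is 5.0% / 4.8% at 0.5 and 4.6% / 4.5% at 0.8. The absolute powers depend on the assumed dropout and patient variance and say nothing about the planned 80%; only the paired differences count.

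**4. Second simulation, both terms together.** Week 16 logistic model, no missing data, 2,000 trials per scenario. Assumptions: 15 or 40 sites, blocks of 4, site SD 0 to 1.0 on the logit scale, EASI log-odds 0 to 0.6 per SD, EASI–vIGA-AD correlation 0.6, 35% with baseline vIGA-AD 4, and vIGA-AD log-odds −0.5. With logistic residual variance π²/3 = 3.29, site SD 0.5 and 1.0 correspond to ICC 0.25/3.54 = 0.07 and 1/4.29 = 0.23.

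- Baseline EASI plus random site gains 0.0 to 3.5 points: 81.4% to 81.4% when neither is prognostic, and 84.8% to 88.3% at site SD 1.0 and EASI log-odds 0.6 (15 sites).
- Type I error is 3.0% to 5.0% for the planned model (3.0% to 4.3% at site SD 1.0) and 4.1% to 5.3% with both terms and random site.
- With site as fixed effects, type I error is 4.4% to 6.1% at 15 sites and 6.4% to 7.6% at 40. With 40 sites, 23% to 48% of patients are in sites with no variation in outcome.

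**The case against.** The strongest reply is that this is optional efficiency. The planned test is valid, and any error effect is on the conservative side. At ICC 0.05 no conservatism is visible, and the gain is under one point. Every input that sets the size is assumed, and in the first simulation patient SD, dropout and the EASI–vIGA-AD correlation were each held at one value. The ICC labels there are best read as weak, moderate and strong site variation, because the value depends on which variances enter the denominator. The largest EASI gain, 4.3 points, arises at 30% versus 45%, while the plan assumes EASI-75 behaves like the vIGA-AD endpoint. EASI-75 is already relative to baseline, so baseline EASI may add nothing. A common severity covariate for both endpoints is a coherent choice and matches the SAP's one prespecified subgroup.

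Most of this stands as a limit on size. It gives no reason to leave the terms out: neither simulation shows a material loss from adding them, even when they are not prognostic.

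Four practical points also stand:
- Only binary models were simulated, so the figures do not cover the MMRM or ordinal models.
- With 40 sites and ICC 0.20 the random intercept moves type I error only from 3.2% to 3.9%.
- Added covariates change the conditional odds ratio being estimated, although the planned model is already conditional on patient.
- The change carries no penalty only in the random-intercept form, as the fixed-effect results show.

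**Conclusion.** The point holds. Site is the sole randomisation stratum and is in no efficacy model. EASI-75 is not adjusted for its own baseline, which is already collected and is used for change in EASI. Neither omission is explained.

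The size is small. In the repeated-measures simulation, site alone gains 0.7 to 3.3 power points over the scenarios run, and baseline EASI alone 0.4 to 2.6 at the planning rates. Both together gain 0 to 3.5 in the Week 16 simulation. Number of sites, between-site variation and the prognostic strength of EASI are assumed, and the gain is close to nil if neither factor matters. With strong site variation the planned test is mildly conservative.

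This is forgone precision, not a shortfall against the 80% power, which was based on an unadjusted test. It also does not offset the either-endpoint success rule or the interim analysis without alpha adjustment, which act in the other direction. The change is worth making because it costs little and aligns the primary analysis with the randomisation. Confidence in the size is medium.

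**What to change.** 1. In SAP 6.1 and 7.3, and in Protocol 12.8.2 and 12.8.3, add site as a random intercept to the efficacy models.
2. For EASI-75, add continuous baseline EASI next to baseline vIGA-AD.
3. Use the same terms in the jump-to-reference imputation model.
4. State that the model is refitted without the site term if it does not converge or the site variance is estimated as zero. A random intercept needs no rule for pooling small sites. Do not enter site as fixed effects if there are many small sites.
5. Fix this before any unblinding, including the optional unblinded interim analysis, and keep the interim SAP consistent with it. Conform the MMRM sentence in the Protocol synopsis.
6. If the sponsor prefers the current model, state why site and baseline EASI are left out.

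The cost is two model terms, a fallback sentence and matching wording. No new data or patients are needed, since site and baseline EASI are already recorded.

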### **11.3 Differentiation of Treatment Failure and AE**

Please note, that the lack of improvement of the symptoms of AD is not an AE and should be reported as treatment failure.

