## 1.5 Randomisation

Approximately 220 patients will be randomized into double-blind treatment groups in a 1:1 ratio by an IWRS.

- 2g DS107 (4 DS107 capsules) administered once-daily for 16 weeks
- Placebo (4 placebo capsules) orally administered once-daily for 16 weeks

A randomization list permuted by blocks and stratified by site will be generated by the Sponsor or its designee. The randomization schedule with study drug assignments will be generated prior to the start of the study and will be known only to the individuals responsible for labelling the study drug, the statisticians generating the schedule and the IWRS team responsible for implementing the schedule. The IWRS will assign a medication kit number to each patient and the contents will be based on the randomization code.

At the investigational site, each patient will be assigned a patient identifier number during screening that will be used on all patient documentation. The patient identifier number will contain the site number and the patient number assigned in numerical order at the Screening Visit (e.g.: 102-10 for the tenth patient screened at the site number 02). Patient numbers will be assigned in ascending order starting with 01.

The treatment assignment procedure will use blocks of sufficient size to maintain a blind and balance across treatment arms. Following successful completion of the screening/baseline evaluations and confirmation that the patient is eligible for participation, the patient will be randomised to treatment. This will be performed by the Investigator using the IWRS which will assign a medication number to the patient.

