The primary statistical analysis assumes “Missing At Random (MAR)” when handling missing data. The treatment effect obtained under the MAR assumption is essentially that which could have been reached if all patients had fully adhered to treatment or, in other words, the effect a patient may expect if they take the medication as directed. This is sometimes known as the ‘de jure’ or ‘efficacy’ estimand. Due to the lack of perfect adherence in practice, the ‘de facto’ or effectiveness treatment effect will also be estimated. This estimand includes assumptions regarding the treatment effects that could be expected to occur when patients discontinue treatment. The jump to reference method described by Carpenter et al. (2013) will be used to estimate the de facto estimand, using the placebo arm as the reference. This is based on the assumption that patients who discontinue from study drug have no alternative oral treatment option suitable for longer-term use and so their responses are likely to revert to those of the placebo group. An additional sensitivity analysis will evaluate patients who received rescue medication as treatment failures from the visit onwards where rescue treatment started. The sensitivity analyses for missing data will be performed on the FAS only.

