### Termination status at end of trial

The incidence and reason for premature study termination (Screening failure, AE, Patient decision (withdrawal of consent to participate), Investigator discretion, Patient lost to follow-up, Lack of efficacy, Pregnancy, Other reasons) will be analysed for the Enrolled Set, i.e. including screening failures and randomised patients, and Safety Analysis Set.

Patients discontinued prematurely will be listed.

The incidence and reason (Violation of Inclusion Criteria X, Violation of Exclusion Criteria Y, Other) for Screening failure will be summarised (using non-randomised subjects of the Enrolled Set only).

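### A patient who withdraws for lack of efficacy without rescue and has no Week 16 value is credited with a positive chance of response in the primary analysis, while a rescue user counts as a non-responder

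*SAP*

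**What the plan says.** **Responder rule.** SAP 6.1 fits a generalised linear mixed model (GLMM), with patient as random effect, to each binary primary endpoint and lets the model deal with missing data. It names one event that fixes the outcome: "If rescue medication is used, the patient will be specified as a non-responder from the time the rescue is used". SAP 7.3 and protocol 12.8.2 and 12.8.3 repeat this, and protocol 9.2.15 calls such patients treatment failures.

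**Missing data.** SAP 4.1.5 assumes missing at random (MAR) for the primary analysis and describes the target as the effect under full adherence, the de jure estimand. A de facto analysis uses jump to reference with placebo as the reference, on the argument that patients stop study drug "so their responses are likely to revert to those of the placebo group". Neither approach distinguishes reasons for leaving. A further sensitivity analysis treats rescue users as failures from the visit at which rescue started (tables 14.2.1.8 and 14.2.1.16).

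**Lack of efficacy.** SAP 7.6 lists it among the recorded termination reasons: "Patient lost to follow-up, Lack of efficacy, Pregnancy, Other reasons". Protocol 7.6 says patients withdrawn for lack of effect are not replaced. Protocol 11.3, in the adverse event chapter, says "the lack of improvement of the symptoms of AD is not an AE and should be reported as treatment failure".

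**Early termination.** Protocol 7.5 asks patients who discontinue to attend as soon as possible for the Week 16 assessments, and section 8.3.6 places that visit under the same heading as Week 16/Visit 7. SAP 4.1.3 takes visits as the database records them. It has no rule on whether an early termination assessment counts as Week 16.

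**The concern.** Consider two patients doing equally badly at Week 8. One is given rescue cream and is a non-responder at Week 16 by rule. The other leaves for lack of efficacy without rescue and has no Week 16 assessment. The GLMM sees only that patient's binary responses so far, not the reason for leaving, and in effect assigns a Week 16 response probability above zero. The outcome depends on how the patient left, not on how the patient fared.

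The other planned analyses do not settle the matter. The rescue sensitivity analysis appears to repeat the rule already in the primary analysis. The per-protocol set takes only patients who completed the study, so it drops these patients. Jump to reference is then the only distinct missing-data check on the full analysis set (FAS), and it too assigns a probability above zero. At stake is the size of the Week 16 treatment difference on both primary endpoints.

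**Working it through.** **1. The plan's own figure.** SAP 2 states: "Assuming a placebo response rate of 12% and a true response rate difference of 15% at Week 16". So placebo is 12% and DS107 27%, with two-sided alpha 0.05. For the chi-square test without continuity correction,

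n per arm = [1.96·√(2·p̄(1−p̄)) + 0.842·√(p₁(1−p₁)+p₂(1−p₂))]² / (p₂−p₁)²

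With p₁ = 0.12, p₂ = 0.27 and p̄ = 0.195 this gives 108.3, rounded up to 109, against 108.4 in the plan's table. The plan says "220 evaluable patients (110 patients per treatment arm) will be needed for 80% power"; at 110 per arm the power is 80.6%. The planning figure reproduces, and 15 points is the yardstick below.

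**2. Assumptions.** The documents give no visit-by-visit response and no withdrawal rate. Assumed:
- response at Weeks 4/8/12/16 of 5/12/20/27% on DS107 and 3/6/9/12% on placebo (the Week 16 values are the design rates);
- a random-intercept logistic model with SD 2, 3 or 4 on the logit scale, visit intercepts solved to match those rates;
- 10% to 20% of each arm leaving for lack of efficacy without rescue, with no Week 16 value.

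**3. Credit per patient.** For a patient with no response at the observed visits,

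P(response at Week 16 | history) = ∫ L(u)·p₁₆(u)·φ(u) du / ∫ L(u)·φ(u) du

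where u is the random intercept, φ its density, L(u) the product of (1 − response probability) over the observed visits and p₁₆(u) the Week 16 response probability. For jump to reference on DS107, p₁₆ uses the placebo intercept. The SAP does not spell out its method for binary data, so that form is also an assumption. With non-response at Weeks 4 and 8:

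| SD | DS107, MAR | Placebo, MAR | DS107, jump to reference |
|---|---|---|---|
| 2 | 0.207 | 0.092 | 0.076 |
| 3 | 0.188 | 0.080 | 0.058 |
| 4 | 0.179 | 0.073 | 0.047 |

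A placebo withdrawal has the same value under MAR and jump to reference, because placebo is the reference.

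**4. Effect on the primary difference.** Excess over counting these patients as failures = d(DS107)·P(DS107) − d(placebo)·P(placebo), where d is the share leaving.
- Equal rates, low end: 0.10 × (0.179 − 0.073) = 1.1 points.
- Equal rates, high end: 0.20 × (0.207 − 0.092) = 2.3 points.
- A model estimate of 15.0 points would become 15.0 − 1.1 = 13.9 or 15.0 − 2.3 = 12.7.
- With Week 12 non-response also observed, the probabilities at SD 4 are 0.120 and 0.052, and at SD 2 they are 0.164 and 0.076. The range is then 0.10 × 0.068 = 0.7 to 0.20 × 0.088 = 1.8 points.

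**5. Direction under unequal withdrawal (DS107/placebo), SD 2.**
- 10%/15%: 0.10 × 0.207 − 0.15 × 0.092 = +0.7 points.
- 5%/15%: 0.05 × 0.207 − 0.15 × 0.092 = −0.3 points.
- Break-even is the ratio of the credits. After two non-responses it is 0.207/0.092 = 2.25 at SD 2 and 0.179/0.073 = 2.45 at SD 4. After three it is 0.164/0.076 = 2.16 at SD 2. So it is about 2.2 to 2.5.

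**6. Jump to reference, equal rates.** 0.10 × (0.076 − 0.092) = −0.2 points and 0.20 × (0.047 − 0.073) = −0.5 points. The credit is smaller on DS107, so the difference shrinks slightly compared with counting failures.

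**7. Crude cross-check ignoring each patient's history.** Take 27% and 12% among patients with Week 16 data.
- At 10%/10%, counting failures gives 0.90 × (27 − 12) = 13.5 points against 15.0 under MAR. At 20%/20% it gives 12.0.
- Jump to reference also gives 13.5 and 12.0.
- At 5%/15%, counting failures gives 0.95 × 27 − 0.85 × 12 = 15.5, above MAR.

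The signs agree with steps 4 and 5. The MAR gap is larger here (1.5 to 3.0 points) because past non-response is ignored.

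**The case against.** **The early termination visit may remove the problem.** If it is stored as Visit 7, a failing patient has an observed value and counts as a non-responder on it. A reader might infer that no planned analysis can ever score such a patient as a failure; the documents do not support that. The objection narrows the point but does not remove it: patients are only asked to attend, the visit may fall well before Day 112 ± 2, and the SAP gives no mapping rule.

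**MAR is a declared estimand choice.** It fits the de jure target. That is fair, but the rescue rule already departs from full adherence, so making the same departure for another sign of failure is no change of principle. A sponsor may still prefer to keep the primary analysis as it is, and the fix allows for that.

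**A reader might infer that jump to reference also flatters DS107.** Step 6 shows that it does not at equal rates. It is more lenient to DS107 than counting failures only if DS107 withdrawals exceed placebo's by about 1.2 times (0.092/0.076) to 1.6 times (0.073/0.047).

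**A reader might infer a built-in bias towards DS107 in the primary analysis.** Credit per patient is larger on DS107, but an effective drug could lose fewer patients for lack of efficacy, and the sign turns at the ratio in step 5.

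**A reader might infer that the SAP breaks protocol 11.3.** It does not. That section tells sites not to report lack of improvement as an adverse event and defines no endpoint outcome.

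**The affected group may be small.** Rescue is available and already fixes the outcome, so only a remainder is concerned. This stands: 10% to 20% per arm is an assumption, not a forecast.

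**The blind data review could deal with it.** SAP 5 lists reason and timing of discontinuation as a topic and allows methodology to be amended there. A rule that decides a primary outcome is better fixed in the SAP.

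**Conclusion.** The gap is real but modest. Rescue use is the only event that makes a patient a non-responder by rule, so an equally failing patient who withdraws for lack of efficacy, without rescue and without a Week 16 value, receives partial credit in the primary GLMM. The likely size is 1 to 2 points on a design difference of 15. This rests on the assumed response paths, random-intercept SD and equal withdrawal of 10% to 20%, and on reading the model's estimate as an average of patient-level response probabilities. Unequal withdrawal can cancel or reverse it. The finding concerns the primary analysis and the unstated handling of early termination visits; jump to reference can stay as planned. It is worth correcting because the correction is cheap and uses data already collected.

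**What to change.** 1. In SAP 6.1 and 7.3 and protocol 12.8.2 and 12.8.3, extend the rescue sentence: a patient whose recorded termination reason is lack of efficacy counts as a non-responder at all later visits in the responder analyses.
2. If the sponsor prefers to keep the de jure primary analysis, run this rule as a pre-specified FAS sensitivity analysis for both endpoints, in place of the rescue analysis that repeats the primary rule (tables 14.2.1.8 and 14.2.1.16).
3. In SAP 4.1.3, state how early termination visits map to analysis visits. For these patients, a visit held before the Week 16 window must not stand as a Week 16 response.

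The cost is a few sentences and no new data. The estimate moves slightly further from the stated de jure effect and will usually be a little smaller.
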